10.6.2 Safety

Safety variables will be analyzed separately for the period between a) Screening and Baseline, b) for the period between Baseline and Month 9, c) for the period between Baseline and final assessment (Month 18 or date of premature withdrawal from the study), d) as well as for the total treatment period (Screening to Month 18). For the randomized treatment period, analyses will be performed according to the treatment group into which the patients were randomized.

All analyzes of safety parameters will be based on the safety population. Corresponding data from the NRP group will be described similarly for the period between Screening and Baseline visit.

The key safety variables which will be analyzed will be as follows.

- Incidence and severity of infections, in particular clinically apparent CMV
- Incidence and severity of Adverse Events (AEs) and Serious Adverse Events (SAEs)
- Incidence of AEs leading to discontinuation from the study
- Relative frequency of abnormal vital signs measurements and laboratory parameters

The incidence rates for (serious) adverse events and infections will be analyzed by treatment group.

AEs/Infections

Generally, infections data are analyzed together with AE data. In addition, infection data will be analyzed separately.

Data collected by AE CRFs and by Infection CRFs and CMV-CRFs are to be coded with the MedDRA dictionary that gives preferred term and body system information. The incidence of AEs will be summarized by body system, preferred term, severity, and relationship to study drug. All information pertaining to AEs noted during the study will be listed by treatment group and patient, detailing verbatim given by the investigator, the preferred term, the body system, start/end dates, severity and drug-relatedness. The AE onset will also be shown relative (in number of days) to the day of initial dose per study period (within the first 3 months, after Baseline (Month 6)).

In addition to being analyzed similarly as AEs, as described above, the relative frequency of infection by type and micro-organism will be tabulated. AEs occurring 7 or more days after the discontinuation of study medication will not be included in AE/infection summary tables.

Laboratory data

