## **2.7 Safety analyses**

### **2.7.1 Adverse events (AEs)**

Safety variables were analyzed separately

- for the period between Screening and Baseline (run-in period)
- for the period between Baseline and Month 9 (switch period)
- for the period between Month 9 and Month 18 (maintenance period)
- for the period between Baseline and final assessment (Month 18 or date of premature withdrawal from the study) (randomized treatment period),.

For the randomized treatment period, analyses of treatment emergent adverse events were performed according to the treatment group into which the patients were randomized.

All analyses of safety parameters were based on the safety population. For the period between Screening and Baseline visit summaries of all adverse events were displayed for the ENR population by randomization status, i.e. randomized versus not randomized patients.

The key safety variables which were analyzed are as follows.

- Incidence and severity of infections, in particular clinically apparent CMV
- Incidence and severity of Adverse Events (AEs) and Serious Adverse Events (SAEs)
- Incidence of AEs leading to discontinuation from the study
- Relative frequency of abnormal vital signs measurements and laboratory parameters

The incidence rates for (serious) adverse events and infections were analyzed by treatment group.

AEs/Infections:

Generally, infections data were analyzed together with AE data. In addition, infection data were analyzed separately.

Data collected by AE CRFs and by Infection CRFs and CMV-CRFs were coded with the MedDRA dictionary that gives preferred term and body system information. The incidence of AEs were summarized by body system, preferred term, severity, and relationship to study drug. All information pertaining to AEs noted during the study were listed by treatment group and patient, detailing verbatim given by the investigator, the preferred term, the body system, start/end dates, severity and drug relatedness. The AE onset was also shown relative (in number of days) to the day of initial dose per study period (within the first 3 months, after Baseline (Month 6)).

In addition to being analyzed similarly as AEs, as described above, the relative frequency of infection by type and micro-organism was tabulated. AEs occurring 30 or more days after the discontinuation of study medication were not included in AE/infection summary tables.

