## 4 Change to protocol specified analyses

Missing data for the primary outcome variable were dealt with the LOCF method according to protocol, but instead of an additional replacement with the mean of the non-missing values, the LOCF2 method (as described in section 2.5.4) as well as repeated measures analysis (see section 2.5.3) were used.

Not randomized patients were considered for the run-in period but not for the randomized treatment period.

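### The SAP counts adverse events to 30 days after stopping where the protocol says 7, does not declare the change, and plans only crude incidence with no stated denominator by period

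*SAP*

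**What the plan says.** Protocol 10.6.2: "AEs occurring 7 or more days after the discontinuation of study medication will not be included in AE/infection summary tables". SAP 2.7.1 has the same sentence with a different number: "AEs occurring 30 or more days after the discontinuation of study medication were not included in AE/infection summary tables".

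SAP section 4 declares two changes to the protocol's analyses. One replaces mean imputation in the missing-data sensitivity analyses, opening with "Missing data for the primary outcome variable were dealt with the LOCF method according to protocol". The other is "Not randomized patients were considered for the run-in period but not for the randomized treatment period". The post-stop cut-off is not listed.

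On the measure, SAP 2.7.1 says "The incidence rates for (serious) adverse events and infections were analyzed by treatment group", and on the analysis set, "All analyses of safety parameters were based on the safety population". Results are to be shown for the run-in, switch, maintenance and whole randomized periods. The section does not say what each percentage is divided by. SAP 5.1.1 adds only that, for a patient who discontinues early, the period runs to the last assessment within it. No person-time or time-to-event method is given for adverse events or infections. For efficacy events, SAP 2.6.2 uses Kaplan-Meier estimates and gives early discontinuation as the reason.

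The stop that starts the window is also unclear. Protocol 10.4.1 defines study medication as everolimus alone and treats the other immunosuppressants as concomitant. SAP 2.1.1 counts cyclosporin, tacrolimus and mycophenolate as study drug too.

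**The concern.** Safety is a secondary objective, and the between-arm comparison of adverse events and infections is read from these tables. A 23-day difference in the cut-off changes which events enter them. The trial is open label and the SAP is dated June 2017, after enrolment closed, so a reader should be able to see that the rule changed and why.

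The second issue does not depend on which window applies. A patient who stops early contributes events for only part of the period. If that patient still counts as one full patient in the denominator, the percentage falls for a reason unrelated to the drug's safety. When stopping differs between arms, part of any difference in incidence reflects a difference in time under count.

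Unequal stopping is plausible here. Only one arm changes regimen after Month 6, and after randomization only that arm's regimen contains mycophenolate, which has its own interruption rules leading to withdrawal from treatment. The documents give no stop rates.

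**Working it through.** **1. The two texts.** The protocol counts events on days 0 to 6 after stopping, the SAP on days 0 to 29. The difference is 30 − 7 = 23 days per patient who stops, provided those days fall within the analysed period. Neither entry in SAP section 4 covers it. At an assumed 0.2 to 1 adverse event per patient-month, 23 days (23/30.4 = 0.76 month) adds about 0.15 to 0.76 events per stopper.

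**2. Effect of truncation on crude incidence.** The documents give no adverse event risk, stop rate or stop timing, so all of these are assumptions:
- true 12-month risk p = 50% in both arms, constant hazard λ = ln 2 / 365 = 0.001899 per day;
- 30% stop in one arm and 15% in the other, uniformly over T = 365 days, unrelated to adverse events;
- counting ends at min(stop day + w, 365), with w = 7 or 30;
- all patients stay in the denominator.

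The chance that a stopper has a counted event is

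m = 1 − (1/T) × [(e^(−λw) − e^(−λT))/λ + w·e^(−λT)].

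- w = 7: m = 1 − (256.3 + 3.5)/365 = 28.8%.
- w = 30: m = 1 − (234.1 + 15.0)/365 = 31.7%.

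Observed incidence = (1 − s)·p + s·m, where s is the share stopping:

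| Window | 30% stop | 15% stop | False difference |
|---|---|---|---|
| 7 days (protocol) | 0.70×50 + 0.30×28.8 = 43.6% | 0.85×50 + 0.15×28.8 = 46.8% | −3.2 points |
| 30 days (SAP) | 0.70×50 + 0.30×31.7 = 44.5% | 0.85×50 + 0.15×31.7 = 47.3% | −2.7 points |

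The differences are taken before rounding. The 162 randomized patients (SAP 1.1) would give 81 per arm if split evenly. Then 2.7 to 3.2 points is 0.027×81 = 2.2 to 0.032×81 = 2.6 patients.

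**3. Range.** Vary the risk (10%, 30%, 50%), stopping (10% v 20%, 30% or 40%) and timing (uniform, or all at day 60), counting 6 and 29 days after the stop. The false difference runs from −0.5 to −11.5 points under the protocol rule and from −0.4 to −10.3 under the SAP rule. The SAP rule gave the smaller distortion in every unequal-stopping case. With 20% stopping in both arms the difference is 0.

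**4. When the direction reverses.** Suppose adverse events cause the stops and every stopper has a counted event. With 30% background risk and 10% v 30% stopping, incidence is 0.9×30 + 10 = 37% v 0.7×30 + 30 = 51%. The arm with more stops now shows more events.

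**5. What person-time does.** In the step 2 example with w = 30, mean counted time for a stopper is T/2 + w − w²/(2T) = 182.5 + 30 − 1.2 = 211.3 days. Per patient this is 0.70×365 + 0.30×211.3 = 318.9 days v 0.85×365 + 0.15×211.3 = 341.9 days, a ratio of 0.933. With identical event rates, events per patient are about 7% lower in the first arm. Events per patient-month, with time ended at the same cut-off, are equal.

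**The case against.** The strongest reply is that the 30-day rule is the better one. Protocol 7.1 collects infections for 30 days after the last dose, so the SAP window matches the data collected, and step 3 shows that it lessens the distortion. The SAP was final before database lock, and protocol 10.1 leaves detail to it. All of this stands. It supports the change but does not declare it. Section 4 exists for that purpose and gives no reason.

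Second, the cut-off limits summary tables only. Serious events are documented until 30 days after the end of participation, discontinued patients are seen again at Month 18, and "All information pertaining to AEs noted during the study were listed by treatment group and patient". Rejection, graft loss, death and MACE have Kaplan-Meier analyses from randomization. Withdrawal or conversion for intolerance is compared between arms. This stands as well, and it confines the point to the adverse event and infection tables. Those tables still carry the comparison for non-rejection safety, and listings do not give a between-arm estimate.

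Third, naming the safety population does not settle the denominator of the switch and maintenance tables, and SAP 5.1.1 leaves it open. A reader might infer that every patient, including those who stopped before Month 9, is counted in the maintenance denominator. The documents do not say so. What they support is that the denominator is undefined.

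**Conclusion.** The 7-day and 30-day rules conflict and the change is undeclared; this follows from the text and needs no assumption. The SAP also plans only crude incidence for adverse events and infections, with truncation after stopping, no person-time measure and no stated denominator by period.

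The size of any distortion is conditional. It is about 3 points under 50% risk and 30% v 15% stopping unrelated to adverse events. It is zero with equal stopping, and the sign can reverse if adverse events drive the stops.

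Three stronger readings are not supported:
- A reader might infer that the move to 30 days makes the arm with more stops look safer. The protocol's own rule already has the effect, and the longer window reduces it.
- A reader might take the mandatory withdrawal for rejection in Months 6 to 9 (protocol 6.5.6) as proof of unequal stopping. The rule applies to both arms.
- For the run-in, SAP 2.7.1 says that "summaries of all adverse events were displayed for the ENR population by randomization status", which may look like a breach of the safety-population rule. That display compares randomized with non-randomized patients and does not touch the comparison of arms.

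**What to change.** 1. List the change from 7 to 30 days in SAP section 4 with its reason, and show the main adverse event and infection table under both windows.
2. Add events per 100 patient-months at risk, by arm, for adverse events, serious adverse events and infections, with time at risk ending at the same cut-off as the events.
3. State the denominator of each period table. Limiting the maintenance table to patients still on treatment at Month 9 should not replace the all-patient table, because it selects on what happened after randomization.
4. Reconcile protocol 10.4.1 with SAP 2.1.1 and state which drug's discontinuation starts the window. This matters because some stops are planned: the CNI in the CNI-free arm, and mycophenolate at Month 6 for patients in the CNI arm who were taking it.

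The cost is SAP wording and a few extra tables from dates and events already collected. No new data are needed.

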### **2.7.1.1 Adverse events of special interest / grouping of AEs**

No adverse events of special interest were defined.

### **2.7.2 Deaths**

Treatment deaths were summarized together with serious treatment emergent adverse events and other significant treatment emergent adverse events by treatment group for the Safety Set (SAF).

Furthermore, deaths were analyzed as composite part of the secondary endpoints treatment failure and major adverse cardiac events for the Full Analysis Set (FAS).

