## **2.2 Analysis sets**

The **Enrolled Patient Population (ENR)** includes all patients who signed an informed consent regardless whether they received study treatment or not.

The **Safety Population (SAF)** consists of all patients who signed an informed consent and who were treated with at least one dose of any immunosuppressive medication after the Screening visit. Note: The statement that a patient had no adverse events constitutes a safety assessment.

The **Randomized Population (RAN)** is defined by all patients who were randomized at Baseline visit. This population will also include patients who were randomized but not treated with the randomized medication.

The **Full Analysis Set (FAS)** consists of all randomized patients who received at least one dose of any immunosuppressive therapy after Baseline Visit (Month 6) and have at least one

post-baseline assessment of the primary outcome variable (renal function based on MDRD method). Randomized patients without data on the primary outcome variable will be excluded from this population; their data will be analyzed for the initial treatment period (up to Month 6) and within the RAN and SAF. Following the intent-to-treat principle, patients will be analyzed according to the treatment group they were assigned to at randomization.

The **Per-protocol Population (PP)** consists of all FAS patients who did not show major deviations from the protocol procedures that may have an impact on the study outcome and who have completed the treatment period at Month 18 according to protocol. Criteria that are assumed to have such an impact were defined before analysis during the Blind Review Meeting and are documented in the Appendix, section 5.6 Rule of exclusion criteria of analysis sets.

For the period before Baseline visit (Month 6) the enrolled patient population was divided by randomization status into randomized patients and not randomized patients.

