### **2.3.1 Patient disposition**

Patient disposition was summarized for all patients by absolute and relative frequencies of patients completing the study phases screening, randomization, treatment and study completion. Reasons for discontinuation of screening, treatment and study were shown by

treatment for all patients (screening) resp. the Randomized Set (treatment and study). The number of patients per analysis set was summarized by treatment.

Protocol violations were reported descriptively by treatment and a listing was generated for each treatment for all screened patients.

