### **2.5.3 Handling of missing values/censoring/discontinuations**

If a patient discontinued from the study prematurely missing data with respect to the target parameter were substituted by the last recorded value (last observation carried forward, LOCF). The LOCF method was only applied if a patient had at least one assessment after Baseline, i.e. on Visits Months 8 to 18. Otherwise, the patient was excluded from efficacy analysis within the FAS population. Prematurely performed month 18 visits were shifted to the closest visit following the date of last observation.

Patients of the FAS population who switched from the CNI group to the CNI-free group during the study or during follow-up, were analyzed in their randomized group.

Additionally, sensitivity analysis was performed with a repeated measurement analysis.

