### **2.6      Analysis of secondary efficacy objective(s)**

#### **2.6.1      Secondary endpoints**

The following secondary efficacy variables were analyzed in an explorative manner:

- Occurrence of treatment failure up to Month 18 defined as composite endpoint of biopsy proven acute rejection of ISHLT 1990 grade  $\geq 3A$  resp. ISHLT 2004 grade  $\geq 2R$ , acute rejection episodes associated with hemodynamic compromise, graft loss / re-transplant, death, loss to follow up (at least one condition must be present).
- Occurrence of MACE and each of its components at Month 18

In addition to the analysis of the primary outcome variable of renal safety and tolerability, the following was analyzed:

- Renal function as assessed by Cockcroft-Gault at month 12 and 18 after Tx
- Serum creatinine and reciprocal creatinine slope (1/serum creatinine versus time) including the treatment period between BL (Month 6) and Month 18

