#### **2.6.2      Statistical hypothesis, model, and method of analysis**

Event data:

Event rates were estimated using the Kaplan-Meier method to handle patients who discontinue the treatment prior to suffering from an event adequately. Time to event was defined as the time from date of randomization to the first documented date of the event. The two groups were compared using the log-rank test.

This procedure was applied for the composite endpoint of treatment failure and each of its components, as well as MACE and each of its components.

Narratives including relevant medical information were provided for each biopsy proven acute rejection, graft loss, or death.

Tolerability:

Analyses of renal function as determined by other calculations (serum creatinine, glomerular filtration rate (GFR, Cockcroft-Gault)) were evaluated in the same manner as described for the primary outcome measure.

The creatinine slope (1 / serum creatinine versus time) was determined from all assessments between Month 6 and Month 18 (both visits included) using a linear regression model. These slopes were compared with a two-sided Wilcoxon ranksum test between the treatment groups.

Additionally, tolerability of study medication was assessed from the rate of patients who withdraw prematurely from study medication or in whom study medication had to be converted to another immunosuppressive regimen due to abnormal laboratory results, adverse events, or toxicity. The frequency distribution of these reasons was presented with absolute and percent values. The most frequent reasons (total  $n \geq 5$ ) for discontinuation and/or conversion as well as the total number of patients who are affected by such intolerance of study medication were compared between the two treatment groups using the exact Fisher test.

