### **2.6.3 Handling of missing values/censoring/discontinuations**

Missing values were imputed with the last observation carried forward (LOCF) method described at section 2.5.3.

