## 5 Appendix

### 5.1 Definitions

#### 5.1.1 Study periods

The following study periods were used for analysis:

- Pre-screening period: Tx – V1/M3/Screening
- Run-in period: V1/M3/Screening – V2/M6/Baseline
- Randomized treatment period: V2/M6/Baseline – V7/M18/EOS
  - Switch period: V2/M6/Baseline – V4/M9
  - Maintenance period: V4/M9 – V7/M18/EOS

In the event of a patient's premature discontinuation, the respective period was defined till the last assessment within this period.

For patients who discontinue prematurely from the study, both, the last available information under study treatment was analyzed.

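### Early deaths can be left out of the log-rank comparison of treatment failure and MACE, because entry to the FAS requires a GFR taken after randomization

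*SAP*

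**What the plan says.** **Population.** SAP 2.7.2, on deaths: "Furthermore, deaths were analyzed as composite part of the secondary endpoints treatment failure and major adverse cardiac events for the Full Analysis Set (FAS". SAP 2.2 defines the FAS as randomized patients with at least one dose of immunosuppression after Month 6 and at least one post-baseline MDRD GFR. Randomized patients without that GFR are "excluded from this population; their data will be analyzed for the initial treatment period (up to Month 6) and within the RAN and SAF". SAP 2.5.3 repeats the exclusion for efficacy: a patient needs "at least one assessment after Baseline, i.e. on Visits Months 8 to 18". The ITT population in protocol 10.2 has the same rule.

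**Endpoint.** SAP 2.6.1 builds treatment failure from biopsy-proven rejection plus "acute rejection episodes associated with hemodynamic compromise, graft loss / re-transplant, death, loss to follow up (at least one condition must be present". SAP 5.1.3 counts any death as a MACE; loss to follow-up is not a MACE component.

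**Clock and test.** SAP 2.6.2: "Time to event was defined as the time from date of randomization to the first documented date of the event". The arms are compared by Kaplan-Meier estimates and the log-rank test, for both composites and for each component.

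Neither SAP 2.6 nor protocol 10.6.1 names an analysis set for these endpoints. The FAS appears only in the sentence on deaths in 2.7.2.

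**The concern.** A time-to-event comparison that starts at randomization should contain everyone who was randomized. Here, entry depends on something that happens later: surviving and being followed up long enough to give a GFR sample. Death is one of the reasons for not giving one, so the entry rule is related to the outcome.

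The interval matters in this trial. Months 6 to 8 fall in the switch period, when the CNI-free arm is being taken off its CNI and the two regimens begin to differ. Protocol section 11 expects the CNI-free regimen to be as safe and effective on exactly these components. If early deaths were unequal between arms, the disposition and safety tables would show it, but the Kaplan-Meier rates and the log-rank test behind the efficacy statement would not.

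**Working it through.** **1. The rules applied to one patient.** Take a patient randomized at Month 6 who dies before giving any post-baseline GFR.

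| Question | Source | Answer |
|---|---|---|
| Is the clock running? | SAP 2.6.2 | Yes, from randomization |
| Is it a treatment failure? | SAP 2.6.1 | Yes, death is a component |
| Is it a MACE? | SAP 5.1.3 | Yes, any death counts |
| Is the patient in the FAS? | SAP 2.2, 2.5.3 | No, there is no post-baseline GFR |
| Is the patient in the log-rank test? | SAP 2.7.2 | No, death in the composites is analysed in the FAS |

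A patient lost to follow-up before any GFR gets the same answers for treatment failure, provided the FAS is used for the whole composite. For MACE, loss is not an event.

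**2. Does another analysis close the gap?** SAP 2.2 promises that these patients are analysed in RAN and SAF. The only analysis that the SAP assigns to the Randomized Set is disposition, where reasons for discontinuation are shown by "treatment for all patients (screening) resp. the Randomized Set (treatment and study". The SAF carries the death summary (2.7.2) and the AE and SAE tables (2.7.1). No time-to-event analysis in RAN is specified.

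**3. Size.** The documents give no event rate, event count or power for treatment failure or MACE, so there is no planned figure to reproduce. The illustration uses 162 randomized patients (SAP 1.1), 1:1 allocation and hence 162/2 = 81 per arm (equal split assumed). Let *f* be the later failures in an arm and *x* the early failures without a GFR, ignoring other censoring:

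- FAS rate = *f* / (81 − *x*)
- RAN rate = (*f* + *x*) / 81

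| *f* (assumed) | *x* = 1: FAS | *x* = 1: RAN | Shortfall (points) | *x* = 2: FAS | *x* = 2: RAN |
|---|---|---|---|---|---|
| 4 | 4/80 = 5.00% | 5/81 = 6.17% | 1.17 | 4/79 = 5.06% | 6/81 = 7.41% |
| 8 | 8/80 = 10.00% | 9/81 = 11.11% | 1.11 | 8/79 = 10.13% | 10/81 = 12.35% |
| 16 | 16/80 = 20.00% | 17/81 = 20.99% | 0.99 | 16/79 = 20.25% | 18/81 = 22.22% |

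With two early failures in one arm, none in the other and the same *f* in both, the between-arm difference in RAN is 2/81 = 2.47 points. In the FAS it is *f*/79 − *f*/81, which gives 0.13, 0.25 and 0.50 points.

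**4. How many patients could be affected?** The scheduled window is 2 of the 12 months at risk. With a constant hazard and an assumed 12-month risk *p* of death or loss, the risk in the window is 1 − (1 − *p*)^(2/12). For *p* = 2%, 5% and 10% this is 0.34%, 0.85% and 1.74%. Times 81, that is 0.27, 0.69 and 1.41 patients per arm. The calculation counts every such patient as having no GFR, so it overstates the number if some gave a sample at an early final visit.

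**5. Effect on the test.** Log-rank p-values on constructed data: 81 per arm, 16 later events in arm A and 8 in arm B, evenly spaced.

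| Early failures, A / B | RAN: A vs B | FAS: A vs B |
|---|---|---|
| 0 / 0 | 19.8% vs 9.9%, p = 0.078 | the same |
| 2 / 0 | 22.2% vs 9.9%, p = 0.032 | 20.3% vs 9.9%, p = 0.067 |
| 0 / 2 | 19.8% vs 12.3%, p = 0.217 | 19.8% vs 10.1%, p = 0.090 |
| 1 / 1 | 21.0% vs 11.1%, p = 0.091 | 20.0% vs 10.0%, p = 0.078 |

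The result can move in either direction, depending on which arm has the early failures. If they are balanced, p changes little and both rates are understated.

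**The case against.** - **The FAS is named only for deaths.** A reader might infer that losses to follow-up are certainly dropped as well. The text does not establish that, because 2.6 names no set. Using the FAS for the whole composite is the natural reading, supported by the efficacy exclusion in 2.5.3, but it remains an inference.
- **Early deaths do not vanish from the report.** A reader might infer that they do. They are in the SAF death summary, and fatal events and MACE are SAEs by definition (protocol 7.6), so they also reach the by-arm SAE tables of SAP 2.7.1. Disposition covers all randomized patients, and a narrative is written for each death. Only the between-arm time-to-event comparison omits them.
- **Early stopping of treatment does not by itself exclude anyone.** The protocol's End of Study visit, with biochemistry, is repeated at early discontinuation. A living patient who attends enters the FAS, provided creatinine, urea and albumin are all available, since SAP 5.1.2 takes every serum value from the visit itself. The affected group is those with no post-baseline GFR at all.
- **The endpoints are exploratory.** They have no margin and no confirmatory test, and the numbers above rest on assumed counts.

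All of this stands and limits the weight of the point. None of it puts an early death back into the log-rank test.

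Two neighbouring matters might be read as part of this one but are separate. SAP 2.6.3 has censoring in its title but says only "Missing values were imputed with the last observation carried forward (LOCF) method described at section 2.5.3", which sets no censoring time; 5.1.1 says that after premature discontinuation "the respective period was defined till the last assessment within this period", without linking this to Kaplan-Meier. Wording in 2.1 and 2.6.2 leans towards on-treatment handling, so a new censoring date or loss-to-follow-up date would be a real choice and not a clarification. Likewise, the 30-day limit on MACE documentation in protocol 7.1 might suggest that later MACE go uncollected. However, the Visit 7 list collects MACE since the last visit without that limit, Visit 7.1 exists for patients who stopped early, and protocol 7.5 and 8.1 require reporting until 30 days after participation ends.

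**Conclusion.** The point holds for deaths on the text of the SAP, and for loss to follow-up within treatment failure if the FAS is used for the whole composite. A rule tied to the outcome removes events from a comparison that starts at randomization, and no RAN version of that comparison is planned.

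The number affected is unknown and may be zero. With 81 per arm and 4 to 16 later failures per arm (both assumed), each omitted early failure lowers that arm's rate by about 1.0 to 1.2 points. Two such failures in one arm only would show as 0.1 to 0.5 points in the FAS against 2.5 in RAN. The direction of any bias cannot be stated in advance. The primary GFR result is unaffected. This is a correction that should be made to the exploratory efficacy comparison; it does not threaten the trial's main conclusion.

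**What to change.** In SAP 2.6.2 and 2.7.2, state that treatment failure, MACE and each of their components are analysed in the Randomized Population (RAN), by randomized arm, with the FAS version as a sensitivity analysis.

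RAN is already defined in SAP 2.2. Death and loss to follow-up are taken from the Study Completion CRF (SAP 5.1.3), which does not depend on a GFR. The cost is a few words, a population flag and one extra set of event tables.

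To be settled separately, not as part of this change: SAP 2.6.3 should state one censoring rule consistent with 2.1 and 2.6.2, and the 30-day MACE sentence in protocol 7.1 should be reconciled with the Visit 7 list and with protocol 7.5 and 8.1.
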